8 PHARMACEUTICAL INFORMATION

8.1 INVESTIGATIONAL AGENT – UBLITUXIMAB

8.1.1 Ublituximab

Chemical Name:	ublituximab
Other Names:	TGTX-1101, LFB-R603
Classification:	Recombinant chimeric anti-CD20 monoclonal antibody
Formulation:	See Investigator Brochure
Mode of Action:	Targets CD20 antigen on B-cells
Description:	Ublituximab is a genetically engineered chimeric murine/human MAb directed against the CD20 antigen found on the surface of B lymphocytes. Ublituximab displays the typical structure of immunoglobulins, consisting of two gamma (γ) heavy chains and two kappa (κ) light chains linked by disulfide bridges. It is composed of a murine variable region (37.2% of total amino acids) fused onto human constant regions.
How Supplied:	Concentration of 10 mg/mL in 3 mL (30 mg) and 15 mL (150 mg) single-use glass vials.
Storage:	Storage Conditions Ublituximab must be stored in a secured limited-access area at a temperature ranging +2°C / + 8°C. Ublituximab must not be frozen.
Stability:	Stability Conditions Once a vial of ublituximab has been opened and/or diluted it must be used immediately. After dilution in polyvinyl chloride (PVC) infusion bags, ublituximab is stable in static conditions for 24 hours at 25°C, and in dynamic conditions it is stable for 8 hours at 25°C. Ublituximab has a shelf-life of 18 months based on available stability data.
Route of Administration:	Intravenous
Packaging:	Ublituximab is packed in unit boxes. Each unit box contains: 
• Five 3 mL or one 15 mL vial(s) containing 10 mg/mL solution of ublituximab• Instructions for dilution in Sodium Chloride 0.9%• A temperature control system including a leaflet with instructions for use The unit boxes containing the 3 mL vial are grouped by 5 in outer package boxes, which will be provided to the clinical trial sites. The unit boxes containing the 15 mL vial are not grouped in outer package boxes and they will be provided individually to the clinical trial sites.

The container closure system of ublituximab is a Type I glass vial closed by a siliconized bromobutyl rubber stopper and a tamperproof protective cap crimped to the neck of the vial.

Availability: Ublituximab is available from TG Therapeutics

8.2 COMPREHENSIVE ADVERSE EVENTS AND POTENTIAL RISKS LISTS (CAEPRS)

8.2.1 Very Common ≥10%

- **Blood and lymphatic system disorders:** Neutropenia, Thrombocytopenia
- **Gastrointestinal disorders:** Nausea
- **General disorders and administration site conditions:** Fever¹, Infusion-Related Reactions, Asthenia, Chills
- **Infections and infestations:** Bronchitis, Nasopharyngitis, Rhinitis, Sinusitis, Oral herpes
- **Investigations:** GGT increased, ALT increased, AST increased
- **Nervous system disorders:** Headache
- **Respiratory, thoracic and mediastinal disorders:** Cough

¹ "Fever" includes preferred terms "pyrexia" and "hyperthermia"

8.2.2 Common ≥1% and <10%

- **Blood and lymphatic system disorders:** Anemia, Pancytopenia, Febrile neutropenia, Autoimmune hemolytic anemia, Macrocytic anemia, Evans syndrome
- **Cardiac disorders:** Cardiac flutter, Nodal arrhythmia
- **Ear and labyrinth disorders:** Tinnitus
- **Endocrine disorders:** Thyroid cyst
- **Eye disorders:** Conjunctivitis, Lacrimation decreased
- **Gastrointestinal disorders:** Lip edema, Gingival bleeding, Oral paresthesias, Stomatitis, Esophagitis, Abdominal pain, Upper Abdominal pain, Gastric ulcer, Constipation, Colonic polyp, Diverticulum intestinal, Diarrhea
- **General disorders and administration site conditions:** Chest pain, Fatigue, Injection site hemorrhage, Peripheral edema
- **Hepatobiliary disorders:** Cholestasis, Cholecystitis acute, Mixed liver injury
- **Immune system disorders:** Drug hypersensitivity, Hypogammaglobulinemia
- **Infections and infestations:** Influenza, Lung infection, Upper respiratory tract infection, Tracheitis, Laryngitis, Tonsillitis, Parotitis, Otitis media, Urinary tract infection, Anal abscess, Bronchopulmonary aspergillosis, Febrile infection, Listeriosis, Septic shock, Staphylococcal sepsis, Streptococcal sepsis, Hepatitis C, Genital herpes, Herpes zoster,
- **Injury, poisoning and procedural complications:** Wrong technique in drug usage process, Head injury, Postoperative hernia, Subcutaneous hematoma
- **Investigations:** Weight decreased, Serum IgA increased, O2 saturation decreased
- **Metabolism and nutrition disorders:** Diabetes mellitus inadequate control, Hypercholesterolemia, Hyperglycemia, Hyperuricemia
- **Musculoskeletal and connective tissue disorders:** Back pain, Musculoskeletal pain, Muscle spasms, Myalgia, Arthralgia, Tendonitis
- **Neoplasms benign, malignant and unspecified (incl cysts and polyps):** Squamous cell carcinoma, Basal cell carcinoma, Leukemia, Neuroendocrine carcinoma of the skin
- **Nervous system disorders:** Somnolence, Paraesthesia, Syncope vasovagal, Ischemic stroke
- **Psychiatric disorders:** Anxiety, Aggression, Depression, Insomnia
- **Renal and urinary disorders:** Hematuria

- **Reproductive system and breast disorders:** Genital prolapse, Vulva cyst
- **Respiratory, thoracic and mediastinal disorders:** Epistaxis, Throat irritation, Bronchopneumopathy
- **Skin and subcutaneous tissue disorders:** Erythema, Urticaria, Allergic dermatitis, Perivascular dermatitis, Skin hemorrhage, Hyperhidrosis, Night sweats
- **Vascular disorders:** Hypertension, Hypotension, Hot flush

8.2.3 Uncommon $\geq 0.1\%$ and $<1\%$

Safety data for ublituximab is only available from administration in 33 patients in the recently completed Phase I clinical trial in relapsed and refractory CLL. As such, due to statistical limitations, no uncommon adverse events (occurring in $\geq 0.1\%$ and $<1\%$ of patients) can be described.

8.2.4 Ordering Ublituximab

Once the clinical trial site receives IRB/EC approval and FDA approval as an Investigator-Initiated (Sponsor) IND a pre-determined quantity of trial drug (UTX) will be shipped from TG Therapeutics to the Investigational Pharmacy at John Hopkins.

Upon receipt of treatment supplies, the Pharmacist or the appropriate person of the site will complete the acknowledgement of receipt and send it back to the TG Therapeutics or designee and update the accountability forms for TG Therapeutics.

If any abnormality on the supplied boxes is observed, the Pharmacist or the appropriate person must document that on the acknowledgement of receipt before sending it to TG Therapeutics or its designee.

8.2.5 Randomization

There is no randomization in this unblinded, open-label safety study.

8.2.6 Dispensing

Before dispensing, the site pharmacist or his/her representative must check that ublituximab is in accordance with the product specifications and the validity is within the re-test and expiry date.

The exact dose and the date and time of administration of ublituximab must be recorded within the CRF, subject's medical records, and/or in the drug accountability records. Batch numbers of ublituximab must be reported within the CRF.

The Pharmacist or his/her representative will record the date dispensed and subject's number and initials on the labels. He/she will complete the accountability forms with information concerning the dispensation of ublituximab. Preparation will be done by the Pharmacist or his/her representative according to instructions for sterile dilution included within the unit boxes of ublituximab. Dilution for ublituximab is as follows:

Dilutions of ublituximab

Ublituximab must not be mixed with other medicinal products. Ublituximab should only be diluted in 0.9% NaCl before use. No data are available for other solutions such as 5% dextrose and 5% mannitol.

Dose of ublituximab for infusion (cohort)	Volume of ublituximab (10 mg/mL)	Volume of NaCl 0.9% to be removed	Final volume in perfusion bag
450 mg	45 mL	45 mL	250 mL

8.2.7 Administration

- IV administration only. Ublituximab should not be administered as an IV push or bolus.
- Ublituximab must be checked before being administered for cloudiness, color, soapy aspect, or deposits.
- Ublituximab must not be administered if does not conform to the specifications. The Investigator or his/her representative must immediately inform TG Therapeutics.
- In accordance with Section 5.1, a list of pre-medication will be administered before infusion of ublituximab.
- Since infusion-related hypotension may occur, **antihypertensive medications may be withheld** 24 hours prior to and throughout infusion of ublituximab
- No other treatment may be co-administered with ublituximab (other than for immediate intervention for adverse event).
- It is recommended that ublituximab be administered immediately after dilution.

Ublituximab should be administered only by slow infusion via intravenous route as a single administration over four (4) hours.

The flow rate is specified in the tables below.

8.2.7.1 Flow Rate for

- T0 to T30': 2% of the total volume
- T30' to T1H: 4% of the total volume
- T1H to T2H: 14% of the total volume
- T2H to T4H: 80% of the total volume

Infusion rate of ublituximab

Ublituximab Dose	Total volume to be infused	Infusion rate			
		T0 to T30'	T30' to T1H	T1H to T2H	T2H to T4H
450 mg	250 mL	10 mL/H	20 mL/H	35 mL/H	100 mL/H

8.2.8 Agent Hypersensitivity

Ublituximab Hypersensitivity and Infusion Reactions: Available at the bedside prior to ublituximab administration will be epinephrine for subcutaneous injection, diphenhydramine hydrochloride for IV injection, and resuscitation equipment for the emergency management of

anaphylactic reactions. Ublituximab should be administered intravenously through a dedicated line.

9 TRIAL CALENDAR/EVALUTION TABLE

Table 6: Schedule of Events

Phase:	Screen (1 day)	Steroid Treatment (5 days)					Plasma Exchange (if necessary)	Follow up		
		1	2	3	4	5		Monthly	90 day	6 month
Day	0	1	2	3	4	5	6-20	30, 60, 90, 120, 150, 180, 210, 240, 270	90	180
MRI of the affected area (brain, c/t spine)	M					M	M		M	
Administration of treatment		Steroids on days 1-5 UTX: 1 dose on day 1 or as early as possible in this phase								
Informed Consent	X									
Eligibility	X									
Demographic, NMO and Medical History	X								X	X
Prior NMO treatments	X									
Vital signs, weight	X	X	X	X	X	X			X	X
Neurological Exam	X	X	X	X	X	X			X	X
Laboratory assessment	X	X	X	X	X			X		X
HCVA		X			X	X			X	X
EDSS		X			X	X			X	X
Timed 25-Foot Walk		X			X	X			X	X
Adverse Events		X	X	X	X	X			X	X
Concomitant Meds	X	X	X	X	X	X				

10 MEASUREMENT OF EFFICACY

This is a primary safety study, but we are interested in recording potential measures of efficacy. These will be assessed as secondary clinical endpoints. Primary outcome measures for safety are detailed in section 12 below.

Efficacy Endpoints

Clinical outcomes will be monitored for efficacy using three functional neurologic tests, the Expanded Disability Status Scale (EDSS), Timed 25-Foot Walk and High Contrast Visual Acuity (HCVA). These will be assessed days 1 and 5 of hospitalization and weekly thereafter for the first three weeks (Days 13 and 20 during PLEX period as needed). In addition, we will use quantifiable MRI parameters as a secondary endpoint as described below.

EDSS

The Kurtzke Expanded Disability Status Scale (EDSS) was developed to measure the disability status of subjects with multiple sclerosis. It allows an objective quantification of the level of functioning that could be widely and reproducibly used by researchers and health care providers. The EDSS provides a total score on a scale that ranges from 0 to 10. The first levels 1.0 to 4.5 refer to people with a high degree of ambulatory ability and the subsequent levels 5.0 to 9.5 refer to the loss of ambulatory ability. The range of main categories include (0) = normal neurologic exam; to (5) = ambulatory without aid or rest for 200 meters; disability severe enough to impair full daily activities; to (10) = death due to MS. In addition, it also provides eight subscale measurements called Functional System (FS) scores. These subscale categories are listed in Appendix 2.

HCVA

High Contrast Visual Acuity: High-contrast Sloan letter charts are readily available and provide a practical, quantitative, and standardized assessment of visual function. Each chart consists of rows of black letters (decreasing in size from top to bottom) on a white background.

For this trial, 100% monocular high contrast visual acuity will be measured on days 1 and 5 during the steroid phase and weekly during the plasma exchange phase. Charts will be read at a 2-meter distance by trained examiners in the hospital room with constant lighting of 80-100 foot-candles accomplished using standard fluorescent hospital room overhead lighting. Binocular testing will be recorded as total number of letters identified correctly (maximum 60).

Timed 25-Foot Walk

Timed 25-foot walking trials will be assessed on days 1 and 5 during the steroid phase and weekly in the plasma exchange phase. The Timed 25-Foot Walk test is a quantitative measure of lower extremity function. If required, the subject may use an appropriate assistive device to walk as quickly as he/she can from one end to the other end of a clearly marked, unobstructed, 25-foot course. Every effort will be made to use the same testing hallway for every Timed 25-Foot Walk test. Potential for external distractions should be kept to a minimum as much as possible. A subject will stand with the toes of his/her shoes on the starting line (identified by a taped mark on the floor) and timing will begin when any part of the subject's foot crosses the tape. Timing will end when any part of the subject's foot crosses the finish line (identified by a taped mark on the floor). Time will be recorded in seconds and rounded to the nearest tenth of a second using a stopwatch provided for this trial. The task is immediately administered again by having the subject walk back the same distance. The average of the two values will be recorded in the case report form.

Objective Efficacy Endpoints

MRIs will be performed for standard of care and research purposes and will be used to make clinical decisions about escalation of immunosuppressive treatment. For this trial, the MRIs will also be analyzed for two parameters: length and T2 hyperintensity in the spinal cord and optic nerve and length of T1 post-contrast enhancement if available.

Number of days in the hospital and requirement for plasma exchange will also be recorded on the CRFs.

10.1 DEFINITIONS

Intent-to-Treat. All subjects who receive one dose of trial drug will be included in the intent-to-treat group.

Per-Protocol. All subjects who performed all visits in accordance with protocol without significant protocol deviations or violations.

All Subject Treatment Group. All subjects who received one dose of trial drug (UTX).

11 STATISTICAL CONSIDERATIONS

This section describes the statistical methods to be used to analyze the efficacy and safety endpoints. A formal statistical analysis plan (SAP), which must be finalized before database lock, will provide additional details for data handling procedures, statistical methods, and data presentations (e.g., table, listing, and figure shells). The final clinical study report will describe deviations from the SAP, if any.

11.1 SAMPLE SIZE

Hypothesis

This trial is exploring the safety of ublituximab in the treatment of NMO/NMOSD relapses. The hypothesis is that the ublituximab regimen proposed in this trial is safe and tolerable in the NMO/NMOSD patient population. The objectives of the trial will be assessed through the use of summary statistics.

Sample Size Considerations

The sample size of 5 subjects is based on feasibility and logistical considerations on the number of subjects that will reveal a significant risk or tolerability issue of using ublituximab + steroids. It is anticipated that 1 subject will fail screening and 1 will drop out over the course of the trial, for a total of 4 subjects who are expected to complete the trial. Subjects who withdraw will not be replaced.

11.2 GENERAL ANALYSIS CONVENTION

Interim Analysis

There will be no interim analysis.

Statistical Analysis

A summary of the number and percentage of subjects with any adverse event, any serious adverse event, adverse events leading to permanent discontinuation of trial drug, and trial drug-related adverse events will be reported.

Change in neurologic outcomes on the EDSS, Timed 25-Foot Walk and HCVA scales from admission to discharge will be analyzed by paired t-tests with significant p-values considered less than 0.05.

By MRI, length of T2 hyperintensity and length of T1-post contrast enhancement should be stable or reduced by discharge. A paired t-test will be used to compare changes in these values with significance considered at p-values less than 0.05.

Continuous data will be described using the following descriptive statistics: n, mean, median, minimum and maximum. Data will be displayed in all listings sorted by subject number.

When count data are presented, the percentage will be suppressed when the count is zero in order to draw attention to the non-zero counts. A row denoted "Missing" will be included in count tabulations where necessary to account for dropouts and missing values. Unless otherwise specified, the denominator for percentages will be the number of subjects with a non-missing assessment within the analysis population of interest.

SAS Version 9.2 will be used to perform all analyses.

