Statistical issues	
Primary Safety Assessments: A summary of the number and percentage of subjects with any adverse event (AE), any serious adverse event (SAE), adverse events leading to permanent discontinuation of trial drug and trial drug-related adverse events will be reported.
 
Secondary Efficacy Assessments: Change in neurologic outcomes on the EDSS, Timed 25-Foot Walk and HCVA scales from admission to discharge (Day 5 or 21), and follow up (Days 90 and 180) will be analyzed by paired t-tests with significant p-values considered less than 0.05. A clinical neurologic improvement is commonly

	observed in > 66% of NMO subjects treated at the Johns Hopkins Hospital. The degree of improvement in this trial population has not been adequately quantified historically. By MRI, length of T2 hyper-intensity and length of T1-post contrast enhancement should be stable or reduced by discharge. A paired t-test will be used to compare these values with significance considered at p-values less than 0.05.
Sample size	The sample size of 5 subjects in this single arm study (UTX + steroid) is based on feasibility and logistical considerations on the number of subjects that will ensure a reliable safety report of ublituximab-mediated B cells depletion in the NMO patient population. An independent Data and Safety Monitoring Board (DSMB) will be composed of five members with at least one member who is an Infectious Disease Specialist, Hematologist, Neurologist, Statistician, and another independent expert with experience on assessing safety. Three of the DSMB members will be on staff at the Johns Hopkins University. The DSMB will be reviewing the safety data after the first two subjects are enrolled and completing the Steroid Treatment Phase to determine if it safe to continue the trial. The DSMB will submit their findings to the Sponsor after every meeting and to the IRB. DSMB meetings can be in-person or via teleconference or a combination of the both. The data to be used for review by the DSMB will be actual raw data recorded in the database. The clinical data will be monitored by TG Therapeutics and will be query-free prior to review by the DSMB.
Duration of Subject Participation	Up to 9 months

Abbreviations and Definition of Terms	
Ab	Antibody
ADCC	Antibody-Dependent Cellular Cytotoxicity
AE	Adverse Event
ALP	Alkaline Phosphatase
ALT	Alanine aminotransferase
AQP4	Aquaporin-4
AST	Aspartate aminotransferase
ATC	Anatomic Therapeutic Class

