11.9 EFFICACY ANALYSES

Secondary endpoints of clinical outcomes will be monitored for efficacy using three functional neurologic tests, the Expanded Disability Status Scale (EDSS), Timed 25-Foot Walk and High Contrast Visual Acuity (HCVA). These will be assessed days 1 and 5 of hospitalization and weekly thereafter for the first three weeks (Days 13 and 20, if needed). The primary analysis will be a change from baseline to Day 90 and the secondary analyses will be a change from baseline to Days 5, 20, and 6 months.

For this secondary efficacy endpoint, the MRIs will be analyzed for two parameters: length of T2 hyperintensity in the spinal cord and optic nerve and length of T1 post-contrast enhancement if available. The secondary analyses for MRI will be a change from baseline to discharge on Day 5 or 20, as well as a change from baseline to follow up at day 90.

Number of days in the hospital and requirement for plasma exchange will be assessed using descriptive statistics.

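### With five subjects and no control arm, p<0.05 paired t-tests at a response-dependent discharge cannot speak to ublituximab, and five subjects cannot guarantee a reliable safety report

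*Combined protocol and SAP*

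**What the plan says.** **Efficacy.** Four places describe the analysis differently.

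- Section 11.1: "The objectives of the trial will be assessed through the use of summary statistics".
- Section 11.2: change in EDSS, Timed 25-Foot Walk and HCVA "from admission to discharge will be analyzed by paired t-tests with significant p-values considered less than 0.05". T2 length and T1 post-contrast length are tested in the same way.
- Synopsis, Statistical issues: change "from admission to discharge (Day 5 or 21), and follow up (Days 90 and 180) will be analyzed by paired t-tests", plus the two MRI lengths.
- Section 11.9: "The primary analysis will be a change from baseline to Day 90", with no test named. For MRI it uses "change from baseline to discharge on Day 5 or 20" and Day 90.

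Section 10 schedules the later in-hospital assessments as "Days 13 and 20 during PLEX period as needed". Section 1.4 recommends plasma exchange for subjects who have not responded by Day 5. The synopsis says clinical improvement is commonly "observed in > 66% of NMO subjects treated at the Johns Hopkins Hospital" and adds that its degree has not been adequately quantified.

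**Safety.** The sample size of five rests on feasibility. The synopsis nevertheless says this number will guarantee a dependable safety report, and section 11.1 says it will bring a significant risk to light. Section 11 states no interval for the safety percentages. Section 11.2 adds that "the percentage will be suppressed when the count is zero in order to draw attention to the non-zero counts".

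**The concern.** The paired t-test asks whether mean change is zero. The protocol already expects it not to be, because most subjects improve on steroids with or without plasma exchange. A p-value below 0.05 would be the predictable result of background recovery, and a reader could take it as a drug effect.

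Discharge makes this worse. Responders are measured at Day 5. Poor responders are measured about two weeks later and after a further therapy. The outcome therefore decides when the outcome is measured.

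On safety, which is the primary objective, a zero count printed without a percentage or interval could be read as absence of risk. With five subjects it says very little.

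**Working it through.** The plan gives no effect size, SD, power or sidedness, so there is no power calculation to reproduce. Tests are taken as two-sided. Five dosed subjects is the figure in the synopsis and section 4.1 (two, then three). Section 11.1 expects 4 completers: 5 − 1 dropout = 4 if the screen failure lies outside the five, but 5 − 1 − 1 = 3 if it lies inside.

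**1. Rejection from background recovery alone (n = 5, alpha 0.05).** Assume normal changes with a proportion p improving, so the standardised mean change is d = Φ⁻¹(p). Rejection follows from the noncentral t with 4 df and noncentrality d√5.

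| Improving on standard care | d | Chance of p<0.05, no drug effect |
|---|---|---|
| 66% (the synopsis floor) | 0.41 | 11% |
| 75% (assumed) | 0.67 | 22% |
| 80% (assumed) | 0.84 | 30% |
| 84% (assumed) | 1.0 | 40% |

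**2. Response-dependent timing.** In a simulation of 200,000 trials, Day 5 change and later change were both normal with mean 0 and SD 1, and subjects with no Day 5 improvement were measured after the later change. All of these are assumptions. With no recovery on average, the chance of a significant improvement is 6.5%, against 2.5% when everyone is measured on a fixed day.

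**3. Number of tests.** Section 11.2: 3 scales + 2 MRI lengths = 5. Synopsis: 3 scales × 3 times + 2 MRI lengths = 11. If nothing changed at all and the tests were independent, the chance of at least one p<0.05 is:

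- 1 − 0.95⁵ = 23%
- 1 − 0.95¹¹ = 43%

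With an assumed common correlation of 0.5 to 0.9 between tests, these fall to about 20–12% and 35–16%.

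**4. What an exact test could show.** The smallest two-sided sign or signed-rank p is 2/2⁵ = 0.0625 with 5 subjects and 2/2⁴ = 0.125 with 4. A two-sided p<0.05 can come only from the t-test's normality assumption.

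**5. Safety: chance of at least one event in five, 1 − (1 − p)⁵.**

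- True rate 10%: 1 − 0.9⁵ = 41%
- True rate 20%: 1 − 0.8⁵ = 67%
- Rate needed for a 95% chance: 1 − 0.05^(1/5) = 45%

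The next figures use the drug-related event rates from the CLL study in section 1.2. That study gave several doses, so they are indicative only. The first four events are those the DSMB follows under section 13.

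| Event | CLL rate | Chance of seeing at least one in five |
|---|---|---|
| Neutropenia | 45% | 95% |
| Thrombocytopenia | 30% | 83% |
| Infection | 27% | 79% |
| Liver enzyme elevation | 18% | 63% |
| Infusion reaction | 61% | 99% |

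**6. Precision.** Clopper-Pearson 95% limits: 0/5 gives 0 to 1 − 0.025^(1/5) = 52%; 1/5 gives 0.5% to 72%.

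**The case against.** The plan never says that p<0.05 would show a ublituximab effect. Section 2.2 speaks of preliminary evidence, section 10 calls this primarily a safety study, and no DSMB or stopping decision uses a p-value. Section 11.9 already makes a fixed day, Day 90, the primary efficacy analysis. Section 11.2 already provides median, range and subject listings, and section 12.5 lists every adverse event by subject. Section 11 defers detail to a later SAP. Five subjects are normal at this stage and would probably show the very common events.

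Much of this is fair as mitigation. The challenge is to the stated claims, not to a small Phase I sample. But the stated aim of description contradicts the significance rule instead of excusing it. A later SAP may add detail, but nothing says it will withdraw protocol text. Day 90 fixes the timing without supplying a control, and section 11.2 does not list it.

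Three qualifications stand.

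- The 11% to 40% figures are illustrative: the synopsis does not say on which scale improvement was judged, and these are rejections because of real recovery, not errors of the test.
- The exact-test floor assumes two-sided testing; a one-sided exact test with five subjects can reach 0.031.
- Efficacy data are dropped for subjects who need additional acute immunosuppression after plasma exchange (section 1.4). A Day 90 summary would inherit that exclusion, which this point does not resolve.

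**Conclusion.** The concern holds. A p<0.05 rule on within-subject change cannot separate ublituximab from steroids, plasma exchange and natural recovery, and pooling two discharge days ties the measurement time to response. The documents also disagree on which analysis applies and on whether the later discharge day is 20 or 21. The rejection rates depend on normality and on the assumed background rate; the conclusion that the test has no usable target does not.

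The safety wording is tenable only for events with true rates near 45% or more. That conclusion needs only five dosed subjects and binomial counts. The trial can run as designed. What should change is how its results are tested, displayed and described.

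**What to change.** 1. In the synopsis and sections 11.2 and 11.9, name change from baseline to Day 90 as the single main efficacy summary, with Day 5 (the scales are scheduled then in all subjects) and Day 180 as supportive. List Day 20 values for plasma exchange subjects only. Do not pool Day 5 with Day 20 or 21 as discharge, and reconcile the two later days.
2. Delete the p<0.05 language. Give individual values, median and range, labelled as change under ublituximab plus steroids with or without plasma exchange. An interval for the mean change is optional and should not be read as a test.
3. In the synopsis and section 11.1, keep the feasibility basis and replace the assurance about safety with wording such as: *Five dosed subjects give a 41% or 67% chance of observing at least one event whose true incidence is 10% or 20%; 0/5 is compatible with a true rate of up to 52%.* If only four are dosed, the figures are 34%, 59% and 60%.
4. Put a Clopper-Pearson 95% interval beside each primary safety percentage in the Safety Population. Exempt that table from the zero-count rule, so that zero prints as 0/5 (0–52%).

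The cost is wording in the synopsis and sections 11.1, 11.2 and 11.9, plus minor programming. No visits or subjects are added. The drawback for the sponsor is that the stated claims become less favourable.
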